11.1.4 Safety Analysis

The following analyses will be based on the Safety Analysis Set.

11.1.4.1 Adverse Events

A treatment-emergent adverse event (TEAE) is defined as an adverse event whose date of onset occurs on or after the start of the study drug. Analyses will be performed for the following TEAE parameters by formulation. TEAEs will be coded using MedDRA dictionary. The frequency distribution will be provided using system organ class and preferred term for each formulation.

- All TEAE
- Drug-related TEAEs
- Intensity of TEAEs
- Intensity of drug-related TEAEs

- TEAEs leading to study drug discontinuation
- Serious TEAEs

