3.0 STUDY SCHEDULE

	Screening period		Administration term									
			Period 1					Period 2				
			Treatment period				Washout period	Treatment period				
Day ¹⁾	Screening -28 to -2	-1	1	2	3	4 ⁹⁾	5 to 20	21	1	2	3	4 ⁹⁾
Days from Period 1 study drug administration ²⁾	-	-	1	2	3	4	5 to 20	21	22	23	24	25
Informed consent	X											
Demographic data, Height	X											
Medical history, concurrent medical conditions, prior medication	X											
Concomitant medication review	X	X	X	X	X	X	X	X	X	X	X	X
Adverse events monitoring ³⁾	X	X	X	X	X	X	X	X	X	X	X	X
Physical examination ⁴⁾	X	X		X		X		X		X		X
Body weight	X	X										
Vital signs ⁵⁾	X	X		X		X		X		X		X
12-lead ECG ⁶⁾	X					X						X
Laboratory tests ⁷⁾	X	X				X		X				X
Pharmacokinetic blood sampling ⁸⁾			X	X	X	X			X	X	X	X
CYP2D6 genotyping blood sampling	X											
Columbia-Suicide Severity Rating Scale (C-SSRS)	X	X				X		X				X
Study drug administration			X						X			
Hospitalization		In				Out		In				Out

- 1) Day 1 is defined as the day of study drug administration in each of Period 1 and Period 2, with the day before Period 1 study drug administration referred to as Day -1 and the day before Period 2 study drug administration as Day 21.
- 2) When the interval between the Period 1 dosing and the Period 2 dosing of the study drug is 3 weeks.
- 3) AEs will be collected continuously from the time of signing of informed consent until the end of Period 2.
- 4) Physical examination will be performed at 24 and 72 hours postdose.
- 5) Vital signs will be measured at 24 and 72 hours postdose.
- 6) A 12-lead ECG will be performed at 72 hours postdose.
- 7) Immunology tests will be performed only at screening. Urine drug tests and pregnancy test will be performed only at screening, Day -1 and Day 21. Pregnancy test will be performed only in female subjects of childbearing potential.
- 8) Pharmacokinetic blood samples will be collected at Day 1 predose, 1, 2, 4, 6, 8, 10, 12, 14, 16, 24, 36, 48 and 72 hours postdose.
- 9) Or at discontinuation.

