9.4 Hospitalization Period

In both Period 1 and Period 2, the subjects will be admitted to the study site on the day before study drug administration, and hospitalized for 5 days. During the hospitalization period, the investigator or sub-investigator will perform assessments and observations of the subjects according to the study schedule shown in Section 3.0. The subjects will be discharged from the study site, after no clinically relevant abnormalities in the physical condition was confirmed based on physical examination in 4 days after study drug administration in both Period 1 and Period 2.

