10.2.4 Start Date

The start date of an AE is the date on which signs or symptoms of the event were first noted by the subject or the investigator or sub-investigator.

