10.2.9.2 AE Reporting

At each study visit, the investigator or sub-investigator will assess whether any subjective AEs have occurred. A neutral question, such as “How have you been feeling since your last visit?” will be asked, and subjects will report any AEs occurring during the study. Subjects experiencing any SAE before first dosing of the study drug must be monitored until the SAE resolves and clinically relevant laboratory abnormalities return to baseline or there is a satisfactory explanation for the observed change. Non-serious AEs occurring before first dosing of the study drug, whether or not related to the study procedure, need not to be followed-up for the purposes of the protocol.

All subjects experiencing AEs after first dosing of the study drug, whether or not related to the study drug, must be monitored until the symptoms resolve and clinically relevant laboratory abnormalities return to baseline or until there is a satisfactory explanation for the observed change. All AEs will be documented on the AE page of the eCRF, whether or not the investigator or sub-investigator concludes that the event is related to the study drug. The following information will be documented for each event:

- Event term
- Start and stop date and time
- Frequency
- Severity
- Investigator’s or sub-investigator’s opinion of the causal relationship to the study drug (related or not related).
- Investigator’s or sub-investigator’s opinion of the causal relationship to study procedures, including details of the suspected procedure
- Action taken with the study drug

- Outcome of event
- Seriousness
- Timing of occurrence (after study drug administration)

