Appendix C Time Windows for Study Procedures

For both Period 1 and Period 2

Test/Observation Item	Scheduled Time	Allowable Time Window
Screening examination ^(a)	Screening (Day -28 to Day -2)	Same as left
Physical examination	Day -1, Day 21	Between 24 hours before administration and just before dosing on Day 1
	24 and 72 hours postdose	±1 hour
Body weight	Day -1	Same as left
Vital signs	Day -1, Day 21	Same as left
	24 and 72 hours postdose	±1 hour
12-lead ECG	72 hours postdose	±1 hour
Laboratory tests	Day -1, Day 21	Same as left
	72 hours postdose	±1 hour ^(b)
Pharmacokinetic blood sampling	Predose on Day 1	Between rising and just before dosing on Day 1
	1, 2, 4, 6, 8, 10, 12, 14, and 16 hours postdose	±5 minutes
	24, 36, 48, and 72 hours postdose	±10 minutes
C-SSRS	Day -1, Day 21	Same as left
	Day 4	Same as left

Day -1 is defined as the day before the Period 1 study drug administration. Day 21 is defined as the day before the Period 2 study drug administration. Day 1 is defined as the day of study drug administration in each of Period 1 and Period 2.

(a) Height, physical examination, body weight, vital signs, 12-lead ECG, laboratory test, blood collection for CYP2D6 genotyping and C-SSRS.

(b) For urinalysis, from the time of rising up to +1 hour of the scheduled time.

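### A treatment-emergent event is defined by onset date although onset time is recorded, so an event before the first tablet on Period 1 Day 1 counts as treatment-emergent under a formulation not yet taken

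*Protocol*

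**What the plan says.** Protocol section 11.1.4.1 calls an event treatment-emergent if it is "an adverse event whose date of onset occurs on or after the start of the study drug". It continues: "Analyses will be performed for the following TEAE parameters by formulation". Section 10.2.4 anchors onset to the calendar day: "The start date of an AE is the date on which signs or symptoms of the event were first noted by the subject" or by the investigator or sub-investigator.

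The data collected are finer than the rule. Section 10.2.9.2 lists "Start and stop date and time" among the items documented for every event, together with an item that begins "Timing of occurrence (after study drug administration".

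Collection covers the hours before each dose. A footnote to the schedule in section 3.0 says that "AEs will be collected continuously from the time of signing of informed consent until the end of Period 2". Section 9.4 says that in both periods "the subjects will be admitted to the study site on the day before study drug administration". Appendix C sets the window for the pre-dose pharmacokinetic sample as "Between rising and just before dosing on Day 1".

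**The concern.** Treatment emergence is meant to separate what happened before exposure from what happened after it. A rule that compares calendar dates cannot do this on the day of the first dose, because that date contains hours on both sides of the tablet. In this study those hours are neither empty nor unobserved: every subject is in the clinic, adverse events are being collected, and a blood sample is taken before dosing. A reaction at the venepuncture site or a faint during that draw would be recorded.

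The secondary objective is safety, and the by-formulation TEAE tables are a main output for it. At stake is whether an event that preceded any exposure is counted as treatment-emergent and shown in a column for a tablet the subject had not yet swallowed.

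**Working it through.** The plan gives no figure to reproduce. The check applies the written rule to each possible timing, and then compares it with the rest of the protocol.

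**Applying the rule**

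| Onset | Date rule (11.1.4.1 as written) | Date-and-time rule | Difference |
|---|---|---|---|
| Period 1 Day 1, before the tablet | TEAE, since the onset date equals the dosing date | Not a TEAE | The flag is wrong, and the only formulation available is one not yet taken |
| Period 1, after the tablet | TEAE | TEAE | None |
| Period 2 Day 1, before the tablet | TEAE, since it follows the Period 1 dose | TEAE | None in the flag; the formulation is wrong only if attribution is also by date |
| Period 2, after the tablet | TEAE | TEAE | None |

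The written definition therefore gives a wrong result in one case, the first.

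**Comparing with other sections.** Elsewhere the protocol divides events at the dose itself, not at midnight:

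- Section 10.2.9.2 exempts non-serious events before the first dose from follow-up and requires monitoring of all events after it. A non-serious event on the morning of Period 1 Day 1 is pre-dose for follow-up, yet a TEAE in the tables.
- Section 10.2.7 codes the action taken as not applicable when the event came before the drug was given. The same event would be pre-dose in the eCRF and treatment-emergent in the analysis.
- Section 10.1 treats a pre-dose event that worsens after initial dosing as a new event. Under the date rule, both a Day 1 pre-dose event and its post-dose worsening would be TEAE records.

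**Size per affected subject.** The planned number is 28 (sections 6.1 and 11.2), and each subject is to receive both formulations, so the planned denominator per formulation is 28. One subject moves an incidence by 1/28 = 3.6 percentage points, provided that subject has no other event in the same table row under the same formulation. If the full add-on of 28 subjects were also pooled, the step would be 1/(28 + 28) = 1/56 = 1.8 points.

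**Size of the time window.** The protocol gives no clock time for dosing. Assume 08:00 to 10:00, which puts 8 to 10 hours of the dosing date before the tablet:

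- against the 72-hour post-dose stay: 8/72 = 11% to 10/72 = 14%;
- against the minimum 3-week interval between doses, 21 × 24 = 504 hours: 8/504 = 1.6% to 10/504 = 2.0%.

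These are shares of observation time, not expected event rates. The protocol gives no event rate.

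**The case against.** The best defence is that this is a matter of drafting. Section 11.1 leaves analysis variables and methods to a statistical analysis plan, which may use onset time. Pre-dose events can also be identified in the data: onset time and timing relative to dosing are recorded, and section 10.2.3 has causality to study procedures assessed separately, so a venepuncture reaction would be marked as procedure-related. The error is also over-inclusive: it adds an event to a descriptive table and never removes one.

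Much of this stands, and it is why the point is minor. It does not remove the point, because section 11.1.4.1 is not silent. It states a rule, that rule is by date, and section 10.2.4 confirms that the start of an event is a date. That pre-dose events can be identified shows that the repair is easy; it does not mean the rule excludes them.

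Three stronger readings are tempting, and the document supports none of them:

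- **Period 2 events go into the wrong column.** Section 11.1.4.1 says that tables are by formulation but not how an event is attributed to one. Misattribution on Period 2 Day 1 is possible if the date logic is carried over, but nothing in the protocol states that it will be. A missing attribution rule can fairly be left to the analysis plan.
- **The drug-related tables are contaminated.** Under section 10.2.2, an event before any drug has been taken should be judged not related, so in Period 1 it should stay out of those tables. A pre-dose event in Period 2 may legitimately be related to the Period 1 dose.
- **A third or more of the dosing-day risk is misclassified.** With dosing assumed at 08:00 to 10:00, 8/24 = 33% to 10/24 = 42% of that calendar date precedes the tablet. That is a share of one day, not of the time over which events are counted.

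**Conclusion.** The point holds for one case. Taken literally, section 11.1.4.1 makes an event before the tablet on Period 1 Day 1 treatment-emergent and leaves only a not-yet-taken formulation to list it under. This contradicts the pre-dose and post-dose distinction in sections 10.1, 10.2.7 and 10.2.9.2. For Period 2 Day 1 the flag is right, and only the formulation is open.

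The consequence is small. The tables exposed are the all-TEAE and intensity tables, with a step of at most 3.6 percentage points per affected subject at 28 per formulation. Few such events are expected. These tables are descriptive, and the bioequivalence assessment in section 11.1.3 does not use them.

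The conclusion rests on reading the definition as written and on the planned denominator. It does not depend on the assumed dosing time.

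**What to change.** In section 11.1.4.1, replace the date criterion with date and time. Suggested wording: *A TEAE is an adverse event with onset date and time at or after the first dose of study drug. Each TEAE is assigned to the formulation most recently taken before onset, by date and time. If the onset time is missing, the onset date alone is used.*

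The first sentence corrects the Period 1 flag. The second closes the Period 2 question before it can arise. The third keeps the present inclusive approach where the time is unknown. Any analysis plan should carry the same definition.

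The cost is a short edit. Onset time and timing relative to dosing are already collected, so no new data or procedures are needed and there is no real downside.

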11.1.4.2 Assessment of Laboratory Data

For continuous variables, the observed values and the changes from baseline will be summarized for each formulation at each visit using descriptive statistics. Case plots will also be presented for the observed values. For categorical variables, shift tables showing the number of subjects in each category at baseline and each post-baseline visit will be provided for each formulation.

11.1.4.3 Vital Signs

For continuous variables, the observed values and the changes from baseline will be summarized for each formulation at each visit using descriptive statistics.

11.1.4.4 Other Safety Parameters

The following analyses will be provided for 12-lead ECGs. For continuous variables, the observed values and the changes from baseline will be summarized for each formulation at each visit using descriptive statistics. Case plots will also be presented for the observed values. For categorical variables, shift tables showing the number of subjects in each category at baseline and each post-baseline visit will be provided for each formulation.

11.2 Determination of Sample Size

Planned number of subjects is 28 (14 per treatment sequence).

The planned sample size was calculated based upon the analysis of logarithmically transformed AUC_{last} and C_{max} . If the 90% CIs for the ratios of Lu AA21004 20 mg tablets and $2 \times$ Lu AA21004 10 mg tablets ($2 \times$ Lu AA21004 10 mg tablets/ Lu AA21004 20 mg tablet) geometric mean value of AUC_{last} and C_{max} are both be within the limits of 80.00% to 125.00%, bioequivalence can be verified. It is hypothesize that there is no interaction between dosing formulation and administration period at AUC_{last} and C_{max} . Based on data from previous studies, the largest estimate of the within-subject coefficient of variation (CV) of AUC_{last} and C_{max} were up to 9.5% and 14.3% and a sample size of 24 would then provide a power of 99.8% and 91.5% for each correctly concluding bioequivalence even if the true ratio is 1.1. Given that the 90% CIs for the ratio of the geometric means for AUC_{last} and C_{max} must both be contained in 80.00% to 125.00% in order to conclude bioequivalence between the two treatments, 24 subjects provided an overall power of at least 91.3%, assuming that the two endpoints AUC_{last} and C_{max} are independent.

Taking into account possible occurrence of dropouts, planned number of subjects is 28.

In case bioequivalence cannot be demonstrated with the number of subjects initially planned due to the insufficiency of the number of subjects, an add-on subject study will be conducted in accordance with the Partial Revision of Guideline for Bioequivalence Studies of Generic Products, if applicable. The maximum number of additional subjects in the add-on subject study is 28 (14 per treatment sequence), which is determined based on study feasibility, but is not on statistical consideration.

12.0 QUALITY CONTROL AND QUALITY ASSURANCE

12.1 Study-Site Monitoring Visits

Monitoring visits to the study site will be made by the sponsor or its designee (contract research organization [CRO]) periodically during the study to ensure that all aspects of the protocol are followed in the conduct of the study. Source documents will be reviewed for verification of data recorded on the eCRFs. Source documents are defined as original documents, data, and records. The investigator and the study site will guarantee access to source documents by the sponsor or its designee and the IRB.

Study documents will be subject to reviews by the sponsor or its designee (as long as blinding is not jeopardized), including the Investigator's Binder, study drug, subjects' medical records, and informed consent documentation, for verification that the study is appropriately conducted in accordance with the protocol. In addition, consistency between eCRFs and related source documents will be checked. It is important that the investigator, sub-investigator and other study personnel are available during the monitoring visits and that sufficient time is devoted to the process.

12.2 Protocol Deviation

The investigator or sub-investigator may deviate and change from the protocol only for medically unavoidable reasons, for example to eliminate an immediate hazard to study subjects, without a prior written agreement with the sponsor or a prior approval from the IRB. In the event of a deviation or change, the investigator should notify the sponsor and the head of the study site of the deviation or change as well as its reason in a written form, and then retain a copy of the written form. When necessary, the investigator may consult and agree with the sponsor on a protocol amendment. If the protocol amendment is appropriate, the amendment proposal should be submitted to the head of the study site as soon as possible and an approval from the IRB should be obtained.

The investigator or sub-investigator should document all protocol deviations.

12.3 Quality Assurance Audits and Regulatory Agency Inspections

The study site also may be subject to quality assurance audits by the sponsor or designees. In this circumstance, the sponsor-designated auditor will contact the site in advance to arrange an auditing visit. The auditor may ask to visit the facilities where laboratory samples are collected, where the medication is stored and prepared, and any other facility used during the study. In addition, there is the possibility that this study may be inspected by regulatory agencies, including those of foreign governments (eg, the Food and Drug Administration [FDA], the United Kingdom Medicines and Healthcare products Regulatory Agency [MHRA], Pharmaceuticals and Medical Devices Agency of Japan [PMDA]). If the study site is contacted for an inspection by a regulatory body, the sponsor should be notified immediately. The investigator and the head of the study site will guarantee access for quality assurance auditors to all study documents as described in Section [12.1](#).

13.0 ETHICAL ASPECTS OF THE STUDY

This study will be conducted with the highest respect for the individual participants (ie, subjects) according to the protocol, the ethical principles that have their origin in the Declaration of Helsinki, and the International Council for Harmonization of Technical Requirements for Pharmaceuticals for Human Use (ICH) Harmonized Tripartite Guideline for GCP. Each investigator will conduct the study according to applicable local or regional regulatory requirements and align his or her conduct in accordance with the “Responsibilities of the Investigator” that are listed in [Appendix A](#).

13.1 IRB Approval

IRBs must be constituted according to the applicable local requirements of each participating region. The sponsor or designee will require documentation noting all names and titles of members who make up the respective IRB. If any member of the IRB has direct participation in this study, written notification regarding his or her absence from voting must also be obtained.

The sponsor or designee will supply relevant documents for submission to the respective IRB for the protocol’s review and approval. This protocol, the Investigator’s Brochure, a copy of the informed consent form, and, if applicable, subject recruitment materials and/or advertisements and other documents required by all applicable laws and regulations, must be submitted to a central or local IRB for approval. The IRB’s written approval of the protocol and subject informed consent form must be obtained and submitted to the sponsor or designee before commencement of the study. The IRB approval must refer to the study by exact protocol title, number, and version date; identify versions of other documents (eg, informed consent form) reviewed; and state the approval date. The sponsor will notify the site once the sponsor has confirmed the adequacy of site regulatory documentation. Until the site receives the notification, no protocol activities including screening may occur.

The study site must adhere to all requirements stipulated by its respective IRB. This may include notification to the IRB regarding protocol amendments, updates to the informed consent form, recruitment materials intended for viewing by subjects, local safety reporting requirements, reports and updates regarding the ongoing review of the study at intervals specified by the respective IRB, and submission of the investigator’s final status report to IRB. All IRB approvals and relevant documentation for these items must be provided to the sponsor or its designee.

Subject incentives should not exert undue influence for participation. Payments to subjects must be approved by the IRB and sponsor.

13.2 Subject Information, Informed Consent, and Subject Authorization

Written consent documents will embody the elements of informed consent as described in the Declaration of Helsinki and the ICH Guidelines for GCP and will be in accordance with all applicable laws and regulations. The informed consent form describes the planned and permitted uses, transfers, and disclosures of the subject’s personal and personal health information for purposes of conducting the study. The informed consent form further explains the nature of the study, its objectives, and potential risks and benefits, as well as the date informed consent is given. The informed consent form will detail the requirements of the participant and the fact that the subject is free to withdraw at any time without giving a reason and without prejudice to further medical care.

The investigator is responsible for the preparation, content, and IRB approval of the informed consent form. The informed consent form must be approved by both the IRB and the sponsor prior to use.

The informed consent form must be written in a language fully comprehensible to the prospective subject. It is the responsibility of the investigator or sub-investigator to explain the detailed elements of the informed consent form to the subject. Information should be given in both oral and written form whenever possible and in the manner deemed appropriate by the IRB.

The subject must be given: (1) opportunity to inquire about details of the study and (2) ample time to decide whether or not to participate in the study. If the subject has decided to participate in the study, then the informed consent form must be signed and dated by the subject before participation in the study. The subject should be instructed to sign using their legal names, not nicknames, using blue or black ballpoint ink. The investigator or sub-investigator must also sign and date the informed consent form prior to subject entering into the study.

The investigator or sub-investigator will retain the original signed informed consent form. The investigator or sub-investigator will document the date the subject signs the informed consent in the subject's medical record. A copy of the signed informed consent form shall be given to the subject.

If the informed consent form is revised, the investigator or sub-investigator will obtain re-consent of the subject in the same manner as the initial informed consent. The date of the re-consent will be recorded in the subject's medical record, and a copy of the revised informed consent form shall be given to the subject.

